**7.1.5. Statistical Analyses / Methods**

Details of the planned displays are provided in [Appendix 10: List of Data Displays](#) and will be based on GSK data standards and statistical principles.

Unless otherwise specified, endpoints / variables defined in Section [7.1.1](#) will be summarised using descriptive statistics, graphically presented (where appropriate) and listed.

**7.1.5.1. Statistical Methodology Specification**

Endpoint / Variables

 
• Proportion of participants with loss of asthma control over Weeks 0-16
 
• Proportion of participants with loss of asthma control over Weeks 0-6 (Secondary)
 

Model Specification

 
• The primary endpoint proportion of subjects with loss of asthma control will be analysed for the Modified Intent-to-Treat excluding GCP non-compliant subjects (Loss of Control) population using both Bayesian (primary) and Frequentist (supportive) methods.
 
 
Bayesian Method (Primary):
 
 
• A logistic regression model within proc MCMC will be used to generate the posterior distribution of the ratio of GSK/Placebo.
 
• The analysis model will include categorical variables for treatment and screening eosinophil strata, with each coefficient (including the intercept) having a non-informative normal(mean=0,var=1x10^6) prior.
 
• Odds ratios generated from the model will be back-transform to produce the probability of experiencing loss of asthma control on both GSK3772847 and Placebo. From these estimates the ratio of loss of asthma control on GSK/Placebo will be calculated within the proc MCMC call.
 

- Three Markov chain Monte Carlo (MCMC) chains will be run, with all parameters in the model being assessed for convergence. This is done to ensure that the results are not sensitive to the initial values selected. The chain with the lowest deviance information criteria (DIC) will be used for the analysis output. Each chain will have 100,000 simulations, with a thinning of 10 and a burn-in of 500, in order to generate 10,000 samples per chain. This may be adjusted if the chains fail to converge. The starting seeds and initial values for all three chains are given below:

	Set Seed	Starting Value
Chain 1	2075971	-2
Chain 2	2075972	0
Chain 3	2075973	2

- The posterior probabilities that the ratio of the proportion of subjects with loss of asthma control on GSK3772847 compared with placebo is less than 1.0, 0.75, 0.7, 0.5 and 0.2 (i.e. more than a 0%, 25%, 30%, 50% and 80% reduction), and greater than 0.6 (i.e. less than a 40% reduction) will be calculated, along with the estimated median ratio and associated 95% credible interval. The 95% credible interval will use the highest posterior density where possible, and if this isn't possible then the 2.5% and 97.5% credible intervals will be reported.
- In addition to summary tables a plot of the cumulative probabilities from the posterior distribution for the ratio of the proportion of subjects with loss of asthma control on GSK3772847 compared with placebo will be generated.
- This analysis will be repeated for loss of asthma control between Weeks 0 and 6.

Frequentist Method (Supportive):

- The proportion of participants with loss of asthma control will be analysed using logistic regression allowing for screening eosinophils strata. It will include fixed effects terms for treatment and screening eosinophil strata.

Fractional Polynomials (Exploratory Analysis for Loss of Control Over Weeks 0-16):

- Screening blood eosinophil count will be transformed using a first order fractional polynomial term, and then a second order fractional polynomial term which will be included in the model as a continuous covariate. A treatment group by transformed eosinophil covariate interaction will also be included in the model to allow the magnitude of the treatment difference to differ by screening eosinophil count.
- The impact of extreme observations are a well-known problem with fraction polynomial modelling. To address this a two-step transformation to “pull-in” extremes and shift the origin away from zero will be used (Royston and Sauerbrei, 2007). The formula to achieve this is given below:

$$g\delta(x) = \delta + (1 - \delta) \frac{g(x) - g(x_{(1)})}{g(x_{(1)}) - g(x_{(2)})}$$

$$\text{where } g(x) = \left[ \ln \left( \frac{\Phi\left(\frac{(x-\mu)}{\delta}\right) + \varepsilon}{1 - \Phi\left(\frac{(x-\mu)}{\delta}\right) + \varepsilon} \right) + \varepsilon^* \right] / (2\varepsilon^*)$$

with:  $0 < \delta < 1$

$$\varepsilon = 0.01$$

$$\varepsilon^* = -\ln [\varepsilon / (1 + \varepsilon)]$$

$$\bar{x} = n^{-1} \sum x_i$$

$$s = (n - 1)^{-1} \sum (x_{(i)} - \bar{x})^2$$

As recommended we shall use  $\varepsilon = 0.01$  and  $\delta = 0.2$ .

- All models (first and second order) will be evaluated and the best fitting model will be selected based on the Akaike information criterion (AIC).
- The selected best fitting model will be used to predict the probability of loss of control by treatment arm along with the corresponding predicted odds ratio by screening eosinophil count. This model will include the observed margins (OM) option which will use the analysis dataset.
- The fit of the model to the raw data will be assessed visually by overlaying a plot of the treatment estimates and differences estimated in groups defined by quartiles of screening eosinophil counts. Estimates will be plotted against the mean eosinophil count within each subgroup.
- The role of baseline immunoglobulin E (IgE) and baseline FeNO (separately) on the effectiveness of GSK3772847 with respect to loss of asthma control will be investigated in a similar way.

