**NOTES:**

- Order represents treatments being presented in TFL, as appropriate.

Treatment comparisons will be displayed as follows using the descriptors as specified:

- GSK3772847 vs Placebo

There were four strata used for the randomisation depending on the participants baseline blood eosinophil count and whether they consented to the sputum sub-study:

- Sputum sub-study and screening blood eosinophils < 150 cells/ $\mu$ L
- Sputum sub-study and screening blood eosinophils  $\geq$ 150 cells/ $\mu$ L
- Not sputum sub-study and screening blood eosinophils < 150 cells/ $\mu$ L
- Not sputum sub-study and screening blood eosinophils  $\geq$ 150 cells/ $\mu$ L

Displays will be presented by combining data across all four strata to give the overall estimate of GSK3772847 versus placebo.

Sputum sub-study will not be accounted for within the statistical analysis as the sputum sub-study strata was for monitoring recruitment only.

An additional exploratory analysis using fractional polynomials has been added to further investigate the relationship between loss of control and screening eosinophils and summary statistics on eosinophils will also be provided.

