### Model Checking & Diagnostics

Bayesian Method (Primary):

- The Markov chain standard error (MCSE) should be compared to the standard deviation of the distribution (SD) to make sure that  $MCSE/SD \leq 0.01$  for all parameters in the mode.
- The Geweke diagnostic test will be used to check whether the mean estimates have converged by comparing means from the early and later part of the Markov chain using a z-score t-test. Large absolute values of the z-score statistic indicate rejection of the null hypothesis of no difference between the mean estimates obtained from the early and latter parts of the chain.
- Gelman & Rubin diagnostic checks should be used to assess if the Markov chains have mixed.
- Visual checks on diagnostic plots will be performed to assess:

- Has the Markov chain settled down?
- Are sufficient simulations being run?
- Is there sufficient burn-in?
- Is the effective sample size large enough?

Frequentist Method (Supportive):

- None.

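### The primary Bayesian analysis keeps one chain picked by DIC, leaves the averaging over eosinophil strata unspecified, and prefers an interval type that depends on the scale of the ratio

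*SAP*

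**What the plan says.** SAP 7.1.5.1 makes a logistic regression in PROC MCMC the primary analysis. On its terms: "The analysis model will include categorical variables for treatment and screening eosinophil strata". On the simulation: "Each chain will have 100,000 simulations, with a thinning of 10 and a burn-in of 500, in order to generate 10,000 samples per chain", followed by "This may be adjusted if the chains fail to converge". On which draws are reported: "The chain with the lowest deviance information criteria (DIC) will be used for the analysis output". The Model Checking & Diagnostics text under the same section requires MCSE/SD of at most 0.01 for every parameter, asks for Gelman-Rubin checks, and asks whether enough simulations were run and whether the effective sample size is large enough. It names no action if the MCSE check fails.

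On forming the ratio: "Odds ratios generated from the model will be back-transform to produce the probability of experiencing loss of asthma control on both GSK3772847 and Placebo". The ratio is then taken from these two probabilities. No stratum level and no weights are given. Section 5.1 sets a general aim: "Displays will be presented by combining data across all four strata to give the overall estimate of GSK3772847 versus placebo".

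On the interval: "The 95% credible interval will use the highest posterior density where possible", with the 2.5% and 97.5% limits as the fallback. Section 2.5 gives a two-sided hypothesis that the ratio is 1. Neither an alpha nor a rule for reading the credible interval is stated. Table 1 in Section 2.1 says that the posterior probabilities of a ratio below 0.70 and above 0.60 were added for internal decisions.

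**The concern.** Three steps between the fitted model and the headline result are chosen without a basis or left open.

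1. **Chain choice.** DIC compares models. Here it is used to choose between repeat simulations of one model, which discards two thirds of the draws and leaves a sample that sits exactly on the plan's own precision limit.
2. **Strata.** With a stratum term there are two probabilities per arm, and an odds ratio alone yields none. Two programmers could follow the text and deliver different ratios and different threshold probabilities.
3. **Interval.** A highest posterior density (HPD) interval is not invariant to transformation. The posterior of a ratio is right-skewed, so on that scale both limits lie nearer to 0 than the equal-tailed limits do.

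At stake are the primary ratio, its interval, and the probabilities meant for internal decisions.

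**Working it through.** **The plan's own figure (Section 2.6).** Inputs: 70 per arm, 44% on placebo, 28% on GSK3772847. Pooled rate (0.44 + 0.28)/2 = 0.36. Standard error = √(0.36 × 0.64 × 2/70) = 0.0811. z = 0.16/0.0811 = 1.97, two-sided p = 0.049. Relative reduction 0.16/0.44 = 36%. The stated figure is reproduced, and its assumptions are used below.

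**1. Chain choice.** MCSE/SD = 1/√ESS, so a limit of 0.01 needs ESS of at least 1/0.01² = 10,000.
- One chain keeps 100,000/10 = 10,000 draws: 0.0100 with zero autocorrelation. If the burn-in of 500 is counted inside the 100,000, it keeps 9,950 draws: 0.01003.
- Simulating the three-coefficient model with the plan's prior, thinning and burn-in, by tuned random-walk Metropolis: ESS about 7,100 to 7,700, MCSE/SD 0.0114 to 0.0119. None of 60 chains passed at any of three proposal scales.
- An independence Metropolis sampler with the same settings gives ESS about 10,000 and MCSE/SD about 0.0100, which is borderline.
- DIC varied between chains with SD 0.06 on a value of 183.1.
- Three chains pooled: ESS about 3 × 7,400 = 22,200, and 1/√22,200 = 0.0067, which passes.
- Effect on results: between-chain SD about 0.002 on the median ratio and 0.005 on P(ratio > 0.6).

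**2. Strata.** For a common odds ratio OR and placebo risk p, the risk ratio is OR/(1 − p + p × OR), so it changes with p. Illustration: 28% v 44% gives OR = (0.28/0.72)/(0.44/0.56) = 0.495. Assume 20% of participants below 150 cells/µL with placebo risk 29%, and 80% at or above 150 with 48%; the placebo average is 0.2 × 0.29 + 0.8 × 0.48 = 44%.
- Below 150: 0.495/(0.71 + 0.29 × 0.495) = 0.58.
- At or above 150: 0.495/(0.52 + 0.48 × 0.495) = 0.65.
- Average: (0.2 × 0.29 × 0.58 + 0.8 × 0.48 × 0.65)/0.442 = 0.64.

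Full posteriors with 31/70 v 20/70 events in all:

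| Assumed strata | Quantity | Lower stratum | Upper stratum | Average |
|---|---|---|---|---|
| 20/80, placebo 29% v 48% | P(ratio > 0.6) | 0.45–0.47 | 0.64 | 0.62 |
| 30/70, moderate effect | median ratio | 0.591 | 0.656 | 0.642 |
| 30/70, moderate effect | P(ratio < 0.7) | 0.73 | 0.62 | 0.65 |
| 30/70, stronger effect | median ratio | 0.515 | 0.660 | 0.642 |
| 30/70, stronger effect | P(ratio < 0.7) | 0.83 | 0.61 | 0.65 |
| 30/70, no stratum effect | median ratio | about 0.64 | about 0.64 | about 0.64 |

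P(ratio < 1) is the same in all three columns. In every draw the ratio is below 1 exactly when the treatment coefficient is negative, whichever stratum is used.

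**3. Interval.** Check without strata: posterior Beta(x, 70 − x) per arm (flat prior on the logit), all outcomes of 70 v 70 enumerated, counting how often the interval excludes 1.

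| True rates | HPD, benefit | HPD, harm | Equal-tailed, each side |
|---|---|---|---|
| 30% both arms | 4.2% | 0.9% | 2.7% |
| 44% both arms | 3.7% | 1.2% | 2.5% |
| 55% both arms | 3.7% | 1.6% | 2.5% |

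The HPD total at 44% is 3.7% + 1.2% = 4.9%. At 20/70 v 31/70, HPD is about 0.37 to 0.97 and excludes 1. Equal-tailed is 0.398 to 1.002 and does not. P(ratio < 1) is 0.974, just short of 0.975. At true rates of 28% v 44%, the upper limit falls below 1 in 58% of trials with HPD and in 51% with equal tails.

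**The case against.** The best defence takes the steps in turn.

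- **Chain choice.** The rule is fixed in advance, cannot be steered by the result, and applies to chains that should already have mixed. The sampler is not named, and one that yields nearly independent draws would sit at the limit. The diagnostics already ask about effective sample size. All of this stands, and it rules out a reading a critic might infer: that the plan cannot meet its own criterion. What remains is that choosing by DIC has no basis, that adjustment is tied to non-convergence, and that a failed MCSE check has no stated consequence.
- **Strata.** A reader might infer that the primary ratio is for a reference stratum and is not averaged. The text does not say so: it names no reference level, and Section 5.1 points to an overall estimate. But it gives no weights, whereas 7.1.5.1 specifies observed margins for the fractional polynomial model and 7.2.4.1 does so for the repeated measures models. The gap is an unspecified step. The sizes above rest on assumed strata and vanish without a stratum effect.
- **Interval.** HPD is a legitimate, pre-specified choice. A reader might infer that it shifts the trial's 5% error toward the drug, or that the interval is the only primary quantity bearing on the hypothesis. Neither is supported: no alpha or interval rule is stated, the total stays near 5%, and P(ratio < 1) is itself a primary output. The 20/70 v 31/70 case is also a close call. The dependence on scale remains.

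**Conclusion.** The concern holds in a limited form. The stratum step matters most: where strata differ in risk, the choice left open moves the ratio and the threshold probabilities, in the assumed 20/80 example by up to 0.64 − 0.45 = 0.19 on P(ratio > 0.6). Most of that comes from using the small lower stratum; using the upper stratum instead of the average moves it only from 0.62 to 0.64. The comparison with 1 through P(ratio < 1) is untouched.

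The chain rule is unsound in principle and leaves no margin on the MCSE limit, but its numerical effect is small. The shortfall figures assume a random-walk sampler.

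The HPD point is secondary. It counts only if the interval is read against 1; then the split under no effect at 44% is about 3.7% for benefit and 1.2% for harm, and the interval can disagree with P(ratio < 1). These figures assume 70 per arm, flat logit priors and no strata.

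**What to change.** In SAP 7.1.5.1:

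1. Replace selection by DIC with pooling of the three chains once convergence is shown (30,000 draws). Apply the MCSE/SD limit to the pooled sample, and state that the chains are lengthened if it fails.
2. State that, in each draw, each analysed participant's probability is predicted under GSK3772847 and under placebo at that participant's own stratum, that these are averaged by treatment, and that the ratio is the ratio of the two averages. Base the threshold probabilities on this ratio.
3. Preferably make the 2.5% to 97.5% interval, already the fallback, the reported one.

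The cost is a few lines of code and wording, with no new data. The third change makes the upper limit slightly less favourable (in the example, 1.002 instead of about 0.97).

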**Table 1 Changes to Protocol Defined Analysis Plan**

Protocol	Reporting & Analysis Plan	
Statistical Analysis Plan	Statistical Analysis Plan	Rationale for Changes
Modified Intent to Treat population.	Modified Intent to Treat (Loss of Control), Modified Intent to Treat and Safety excluding GCP non-compliant subjects populations.	The Modified Intent to Treat (Loss of Control) was added to account for the intercurrent event when participants receive the wrong study treatment. Whilst the data from GCP non-compliant participants should not be used in the efficacy analysis, the participants were dosed with GSK3772847 or Placebo so all safety data (AEs, SAEs, ECGs etc.) should be reported.
Section 10.4.1 of the protocol describes a sensitivity analysis where data is analysed as missing and worst case (loss of control) for participants who withdraw from the study for reasons other than loss of asthma control.	A primary and secondary estimand have been defined to capture where data is analysed as missing and worst case (loss of control) for various intercurrent events where participants withdraw from the study for reasons other than loss of asthma control.	The protocol was approved before the ICH E9 addendum on estimands. The RAP is performing the same planned analysis as detailed in the Protocol however the terminology has been updated in accordance with ICH E9.
Statistical analysis would be performed for each screening eosinophil strata separately.	Bayesian analysis will include screening eosinophil strata as a covariate instead of performing split analysis models.  In addition, an exploratory analysis using fractional polynomials was added to examine the relationship between loss of control and screening eosinophils (continuous), IgE and FeNO.	Bayesian analysis will now include the same covariates as the frequentist analysis.  By modelling eosinophils as a continuous endpoint, it will provide more information on the impact of varying screening eosinophil levels on the treatment effect. It will also provide additional information on the role of IgE and FeNO on loss of asthma control.

Protocol	Reporting & Analysis Plan	
Statistical Analysis Plan	Statistical Analysis Plan	Rationale for Changes

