**Fractional Polynomials (Exploratory Analysis)**

The role of free sST2 on the effectiveness of GSK3772847 with respect to loss of asthma control will be investigated, using the modified intent to treat (loss of control) population. The number of participants experiencing loss of control will be predicted at each level of baseline free sST2 based on a model including a free sST2 main effect term and an interaction with treatment term.

Baseline free sST2 will be transformed using a first order fractional polynomial term, and then a second order fractional polynomial term which will be included in the model as a continuous covariate. A treatment group by transformed free sST2 covariate interaction will also be included in the model to allow the magnitude of the treatment difference to differ by baseline free sST2.

The impact of extreme observations are a well-known problem with fraction polynomial modelling. To address this a two-step transformation to “pull-in” extremes and shift the origin away from zero will be used (Royston and Sauerbrei, 2007). The formula to achieve this is given below:

$$g\delta(x) = \delta + (1 - \delta) \frac{g(x) - g(x_{(2)})}{g(x_{(1)}) - g(x_{(2)})}$$

$$\text{where } g(x) = \left[ \ln \left( \frac{\Phi\left(\frac{(x-R)}{\varepsilon}\right) + \varepsilon}{1 - \Phi\left(\frac{(x-R)}{\varepsilon}\right) + \varepsilon} \right) + \varepsilon^* \right] / (2\varepsilon^*)$$

with:  $0 < \delta < 1$

$\varepsilon = 0.01$

$\varepsilon^* = -\ln [\varepsilon/(1 + \varepsilon)]$

$$\bar{x} = n^{-1} \sum x_i$$

$$s = (n-1)^{-1} \sum (x_{(i)} - \bar{x})^2$$

As recommended we shall use  $\alpha = 0.01$  and  $\delta = 0.2$ .

All models (first and second order) will be evaluated and the best fitting model will be selected based on the AIC.

The selected best fitting model will be used to predict the probability of loss of control by treatment arm along with the corresponding predicted odds ratio by baseline free sST2. This model will include the OM option which will use the analysis dataset.

The fit of the model to the raw data will be assessed visually by overlaying a plot of the treatment estimates and differences estimated in groups defined by quartiles of baseline free sST2 counts. Estimates will be plotted against the mean baseline free sST2 count within each subgroup.

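### The exploratory fractional polynomial analyses choose only among models with a treatment-by-biomarker interaction, so the fitted curve cannot show a constant drug effect, and nothing is specified to tell real modification from noise

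*SAP*

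**What the plan says.** References are to the amended plan, which comes first in the SAP file. In section 7.1.5.1, screening eosinophils enter as a first-order and then a second-order fractional polynomial, and "A treatment group by transformed eosinophil covariate interaction will also be included in the model". The selection step is "All models (first and second order) will be evaluated and the best fitting model will be selected based on the Akaike information criterion (AIC"). The chosen model is then used to "predict the probability of loss of control by treatment arm along with the corresponding predicted odds ratio by screening eosinophil count".

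The same approach is applied elsewhere:
- Section 7.1.5.1 extends it to two more markers: "The role of baseline immunoglobulin E (IgE) and baseline FeNO (separately) on the effectiveness of GSK3772847" is to be studied in a similar way.
- Section 7.2.4.1 repeats it for Week 4 FEV1.
- The free sST2 analysis after section 10.1.5 predicts loss of control "based on a model including a free sST2 main effect term and an interaction with treatment term", and adds: "A treatment group by transformed free sST2 covariate interaction will also be included in the model".

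The only check on the result is graphical: "The fit of the model to the raw data will be assessed visually by overlaying a plot of the treatment estimates and differences", using quartile groups of the same data. The results presentation in 7.1.5.1 asks for a plot and mentions no interaction p-value or interval for it. Section 2.1, Table 1 gives the purpose of treating eosinophils as continuous: "it will provide more information on the impact of varying screening eosinophil levels on the treatment effect". The analyses are labelled exploratory throughout.

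**The concern.** Table 1 wants to learn how the drug effect changes with the biomarker. The first question is then whether it changes at all, and the procedure cannot answer it. AIC is asked which shape of variation fits best, never whether any variation is needed. With about 140 participants and a binary outcome, even a constant effect will produce a sloping or curved odds ratio, often a steep one. The quartile overlay does not help, because it shows that the curve follows the data, noise included. At stake is how Figures 2.12 to 2.33 and 6.9 to 6.12 are read. A reader could see an apparent group of good responders, or a range of apparent harm, with nothing on the page showing how often such a picture arises by chance.

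**Working it through.** **1. The plan's own design figure.** Section 2.6 gives 70 evaluable participants per arm, 44% on placebo and 28% on GSK3772847 as the smallest effect that rejects the null hypothesis. Relative reduction: (0.44 − 0.28)/0.44 = 36.4%. Pooled z: 0.16/√(0.36 × 0.64 × 2/70) = 0.16/0.0811 = 1.97. Unpooled z: 0.16/√((0.44 × 0.56 + 0.28 × 0.72)/70) = 0.16/0.08 = 2.00. The stated 36% and 28% reproduce at two-sided 5%. These rates supply the simulation inputs. Odds ratio: (0.28/0.72)/(0.44/0.56) = 0.495.

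**2. Structure.** In every candidate the log odds ratio at biomarker value x is β + Σ γⱼ x^(pⱼ), with one γ (first order) or two (second order). It is constant only if every estimated γ is exactly zero, which does not happen in practice. Without the interaction it is simply β, and no such model is in the set. This needs no assumption about the data.

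**3. Size when the true odds ratio is constant.** The SAP does not give the power set or the biomarker distribution. Assumed: powers −2, −1, −0.5, 0, 0.5, 1, 2, 3, giving 8 first-order and 28 + 8 = 36 second-order models. The biomarker is lognormal with median 250 cells/µL and log-SD 0.8 in the 700-trial run. The plan's preliminary transformation is applied with ε = 0.01 and δ = 0.2, dividing by the standard deviation. Each model has treatment, polynomial terms and their interaction, and the lowest AIC wins. The table gives the max/min ratio of the predicted odds ratio over the 10th to 90th percentiles, 70 per arm.

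| Setting | ≥2-fold | ≥3-fold | Crosses 1 |
|---|---|---|---|
| AIC rule, 44% v 28%, 700 trials | 62% | 43% | 28% |
| AIC rule, 44% v 28%, 250 trials | 58% | 38% | 28% |
| AIC rule, 44% v 28%, 200 trials | 61% | 42% | 30% |
| AIC rule, 44% v 44%, 700 trials | 60% | 39% | 65% |
| One log-linear interaction, no search, 44% v 28%, 4000 trials | 48% | 27% | 22% |
| Same, 200 trials | 50% | 24% | 21% |

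The three 44% v 28% runs of the AIC rule agree within simulation error: for the first column, √(0.62 × 0.38/700) = 1.8 points, 3.1 points at 250 trials and 3.4 at 200. The search adds 62 − 48 = 14 points at the 2-fold mark, or 61 − 50 = 11 in the smaller pair.

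Over the wider 5th to 95th percentile range (geometric SD 2, 1500 trials), the figures are 74%, 59% and 42%. The median ratio is 3.8 (IQR 1.9 to 8.8), and no curve was flat. At 500 per arm the median falls to 1.6, still never flat.

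**4. What a comparator and a test would do.** Parameter counts including the intercept: treatment only 2; treatment plus polynomial main effect 3 or 4; with interaction 4 or 6. With the no-interaction models added under plain AIC, a varying effect is still chosen in 19% to 23% of constant-effect trials at 70 per arm. Charging one extra parameter per searched power selects a constant effect in 86% to 91%. A likelihood-ratio test of the interaction that treats the selected powers as fixed rejects in 15% to 17% at a nominal 5%, so an ordinary p-value would not be a fair test.

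For Week 4 FEV1 only step 2 applies. No size was simulated, because the plan gives no FEV1 variance.

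**The case against.** The strongest reply is that the plan promises little here. The interaction is there to let the effect vary, AIC picks a curve shape, the output is a figure, and the label is exploratory. No threshold, claim or decision depends on it. A constant odds ratio with 95% confidence interval and p-value is already reported from the supportive logistic model (Tables 2.5 and 2.7). Noise on this scale is also ordinary at this size: raw quartile odds ratios differed at least 2-fold in 91% of simulated constant-effect trials. All of this stands, and it limits the point to how the curves can be read. It does not supply what is missing. The supportive model is never compared with the curve, and a quartile overlay that is itself this noisy cannot confirm it.

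A reader might infer more than the document supports:
- **That the plan declares effect modification in every trial.** It plots an estimate and declares nothing.
- **That these models replaced the separate-stratum analyses.** In Table 1 the split Bayesian models gave way to strata as a covariate, and the fractional polynomial work was an addition.
- **That the figures will steer enrichment or dose choice.** Nothing links them to either, and there is one active dose.
- **That the preliminary transformation divides by a variance, because s is printed without a square root.** The equations are damaged in extraction, and the divisor inside the normal distribution function reads differently in each of the three copies. This cannot be charged to the plan.

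**Conclusion.** The point holds as a limited, worthwhile correction. As specified, the selected curve cannot show a constant effect, and no test or comparator says whether the variation exceeds chance. That follows from the text alone. The size is conditional: about 60% of constant-effect trials show at least 2-fold variation across the 10th to 90th percentiles at about 70 per arm, against about 50% with one pre-specified log-linear interaction. Most of the spread is therefore sampling noise, not a product of the AIC search. The percentages depend on the assumed lognormal biomarker, the usual power set and the percentile range, and the 2-fold mark is a chosen yardstick. Whether confidence bands are planned is unknown, since the figure shells are not in the document. The primary comparison is unaffected.

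**What to change.** In sections 7.1.5.1, 7.2.4.1 and 10.1.5:

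1. Fit as comparators the matching models without the interaction: treatment only, and treatment plus each fractional polynomial main effect. If AIC is used for this comparison, charge one extra parameter per searched power, since plain AIC still prefers a varying effect in about one constant-effect trial in five.
2. For each biomarker, report an interaction p-value that allows for the power search, for example a parametric bootstrap under the best constant-effect model that repeats the search in each sample.
3. Show the constant odds ratio (or FEV1 difference) and confidence bands beside each curve.
4. State that no effect modification is shown when the comparator is preferred or the test is not significant.

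The cost is SAP wording and a little programming, with no new data, and every planned curve is kept. The downside is that weak true modification may be labelled as not shown, so that label should not be read as evidence that the effect is constant.
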